**VERSION NUMBER: 10**

**VERSION DATE: May 3, 2018**

**OBJECTIVES:**

The primary purpose of this pilot study is to test a novel head worn light device (Re-Timer®) as an intervention to improve glucose metabolism in people with prediabetes. The hypothesis is that morning light treatment will improve glucose metabolism. This is a pilot study and the data from this project will be used to develop a larger clinical trial.

**BACKGROUND:**

**Circadian Misalignment Impacts Risk for Type 2 Diabetes**

The central circadian clock, which regulates many circadian rhythms, is located in the suprachiasmatic nuclei (SCN, ). In humans, central circadian timing is most reliably estimated from the onset of melatonin secretion in dim light (DLMO ), which occurs ~2-3 h before habitual bedtime . Melatonin must be measured in dim light because it is suppressed by light . In most humans (>70%), the endogenous period of the central circadian clock is greater than 24 h , resulting in an endogenous tendency to drift later each day (phase delay). Such drift can result in a mismatch between behavioral cycles (sleep-wake and meal times) and internal biological time, known as “circadian misalignment”. There is evidence indicating that circadian misalignment is associated with increased diabetes risk and worse diabetic outcomes. Later sleep timing or self-reported eveningness (suggestive of circadian misalignment) is positively associated with obesity , and T2DM (OR 1.73-2.5, ), and predictive of future increases in BMI , even after adjusting for potentially confounding variables such as age, sex, race, SES, physical activity and sleep duration. Later sleep timing is also associated with reduced glycemic control (higher HbA1c) in patients with T2DM , even after adjusting for age, sex, race, BMI, insulin use, depression, sleep debt and diabetes complications.

Laboratory studies have also investigated the effects of circadian misalignment on diabetes risk in healthy humans. In one study, circadian misalignment resulted in an overall 6% increase in 28 h levels of glucose, despite a 22% increase in insulin, and 3 out of 8 subjects exhibited 2-h postprandial glucose responses >140- <210 mg/dl (prediabetic or diabetic levels) . In a second study, circadian misalignment resulted in an 8% increase in glucose but 12% decrease in insulin (fasting), and a 14% increase in glucose but 27% decrease in insulin (postprandial) . However, in these studies circadian misalignment also disrupted sleep, and disrupted sleep can impair glucose metabolism . A third study examined less severe circadian misalignment (2 x 2 daytime sleep episodes interspersed with night-time sleep) and controlled for sleep by

comparing to a control condition with equivalent sleep loss. They found that circadian misalignment, independent of sleep loss, resulted in an additional 26% reduction in insulin sensitivity in men, with no compensatory increases in insulin release, reflecting a significant increased risk of T2DM. The authors concluded “this provides evidence in support of an intrinsic adverse effect of circadian misalignment on glucose metabolism.” (p1868, ).

The precise mechanism(s) by which changes in circadian timing could affect metabolism remain to be determined, but may include: (1) direct impact of SCN activity on glucose regulation via multisynaptic projections from the SCN to the liver and pancreas, (2) suppressed melatonin levels (light exposure during night), which is independently associated with increased insulin resistance in nondiabetics and the development of T2DM. Indeed, the melatonin receptors on pancreatic beta-cells preserve beta-cell function by preventing “functional overcharge”, (3) circadian misalignment results in peripheral molecular dysfunction, which downstream in the pancreas and liver can adversely impact diabetes risk. Thus, “dysregulation of circadian secretion may be a key to the increase of T2DM” (p829, ).

### **The Effect of Morning Light Treatment on Glucose Metabolism Remains to be Investigated**

Light is the strongest environmental signal that can alter circadian timing. Light is captured by the 5 retinal photoreceptors (rods, 3 cones, and the intrinsically photosensitive retinal ganglion cells [ipRGCs]). The ipRGCs are the primary circadian photoreceptor as they transmit the light signal directly to the SCN. The ipRGCs are most sensitive to short (~480 nm) wavelengths of light. Evening light shifts circadian timing later (phase delays) and can exacerbate the endogenous tendency towards circadian misalignment. By reducing exposure to evening light, there is potential to phase advance circadian timing. Conversely, morning light shifts the clock earlier (phase advance), and helps to realign circadian timing to more closely match the external environment, and reduce circadian misalignment. Thus, morning light is the most important light most humans receive every day.

[figure not shown]
Given the associations between later sleep/circadian timing and risk for T2DM, one would expect morning light to be associated with a reduction in risk for T2DM. Four studies have examined these relationships. The first reported that the addition of daily morning light (1 h, 5,000 lux) to a 6 week exercise program in 17 overweight/obese people led to a significant reduction in body fat that did not occur with exercise alone. A second study reported that daily morning light (45 mins, 1300 lux) for 3 weeks significantly reduced body fat and appetite in 34 overweight women. The reduction in body fat was seen after 2 weeks of morning light treatment. A third study reported that a single dose of morning light (2 h, 60 lux) changed appetite regulating hormones (leptin, ghrelin) in a direction that would reduce hunger in 11 sleep deprived subjects. Last year, a study of healthy individuals reported that brighter light exposure (>500 lux) earlier in the day independently predicted a lower BMI, even after adjusting for age, sex, season, activity and sleep duration. All these studies point to the high potential for morning light treatment to reduce risk for T2DM, and highlight that many of the effects of morning light were observed in small sample sizes. Indeed, as others have recently stated: (1) “prescribed light exposure needs to be tested for its ability to restore the physiological dialogue between circadian mechanisms and metabolic pathways” (p7, ) and (2) “interventional studies assessing the role of manipulating the master clock in the treatment of T2D are needed...the master clock can be manipulated by light therapy” (p326, ).

### **Preliminary Data**

#### **Later Circadian Timing is Associated with Increased Risk for Type 2 Diabetes**

Drs. [name] and [name] collaborate on an ongoing R01 project to examine the cross-sectional association between sleep/circadian timing and diabetes risk in persons without

diabetes. We examined the associations between the timing of sleep based on 1-week of actigraphy (average midpoint of sleep) and circadian timing (gold standard circadian phase marker in humans, DLMO), and fasting glucose levels in the first 20 subjects with data (Figure 1). Results indicate that later sleep/circadian timing is significantly associated with higher fasting glucose even in those who do not currently have diabetes. These data are entirely consistent with the literature and represent the first data examining the relationship between the DLMO and fasting glucose.

### Creating a Placebo Light Treatment

We now plan to test an active Re-timer® versus a placebo Re-timer®. We first considered creating a placebo Retimer® by retrofitting the Re-timer® with red LEDs (~660 nm), as this wavelength is further from the maximum sensitivity of the ipRGCs. However, this would have required additional ocular and electrical safety testing. Furthermore, subjects would have quickly discovered the red Re-timers® were not standard treatment, as we find many subjects look up their light devices on the internet. Thus, it appeared likely that subject expectations would have differed significantly between the standard versus red Re-timer®. Therefore, we enlisted the help of [name] from Rush University (consultant on this grant), who used neutral density filters to markedly reduce the light intensity of the Re-timers® to a level that will not shift circadian timing. There are no safety concerns because the light from the already safety approved Re-timer® has simply been dimmed. [name] spectroradiometer recordings confirm that irradiance in these dimmed Re-timers® is reduced from 230  $\mu\text{W}/\text{m}^2$  to 3  $\mu\text{W}/\text{m}^2$ , and lux reduced from 500 lux to 7 lux (Figure 2). Importantly, the placebo (dimmed) Re-timers® appear identical to those featured on the Re-timer® website and so are a highly believable placebo that should lead to similar expectations between treatment groups.

[figure not shown]

Figure 2. Spectral power distribution of the active vs. placebo Re-Timer® measured with a PR670 spectroradiometer with a 2nm resolution.

### Measures of Compliance to Light Treatment

[name] (Rush University PI) developed a measure of compliance to the Re-timer®, as none exists. By securing an Actiwatch Spectrum to the inside of the Re-timer® (does not unbalance frame), she can examine (1) green light to determine active Re-timer® on/off times and (2) activity to confirm both placebo and active Re-timers® are worn at the assigned times.

### INCLUSION AND EXCLUSION CRITERIA:

We will enroll 34 subjects (50% female, age 35-70 y) with prediabetes to complete the study. Laboratory sessions will occur during women's follicular phase or women will be postmenopausal ( $\geq 6$  months since last menses). These subjects will: (1) be overweight or obese ( $BMI \geq 25 \text{ kg/m}^2$ ), (2) have prediabetes ( $HbA1c 5.7\% \text{ to } < 6.5\%$ ), and (3) be free of severe obstructive sleep apnea (apnea-hypopnea index  $< 30$ ). The laboratory sessions will occur during women's follicular phase or women will be postmenopausal ( $\geq 6$  months since last menses). Women on oral contraceptives or hormone replacement therapy will be excluded (alters OGTT  and melatonin ). We will also exclude women who are pregnant, planning on becoming pregnant, or are breastfeeding. We will exclude men and women who have a child at home that does not sleep through the night. Adults unable to consent, individuals who are not yet adults (infants, children, teenagers), pregnant women, and prisoners are also excluded.

Additional exclusion criteria include: history of type 1 or type 2 diabetes, use of diabetes medications, age outside 35-70 years (we will not enroll anyone older than 70 years because of a reduced response to light ), smokers, shift workers, failing urine drug test (drugs of abuse, nicotine), eye disease, photosensitizing medications, regular hypnotic use ( $\geq 3$  nights/week), daily beta-blocker, NSAID or melatonin use (confounds DLMO), history of the following psychiatric disorders (confounds effect of light treatment, per relevant items from Mood Disorder, Psychotic Screening and Substance Use Disorders Modules of the Structured Clinical Interview for DSM-IV Axis I Disorders - Non-Patient Edition (SCID-IV/NP; ): schizophrenia, bipolar depression, substance abuse, suicidal ideation, or obsessive compulsive disorder, PTSD). At screening subjects who score  $> 20$  on the Center for Epidemiologic Studies – Depression (CES-D) scale  will also be excluded. Additional exclusion criteria include irregular menses, history of cardiovascular disease (excluding hypertension), endocrine, kidney, gastrointestinal or liver disorder, seizures, and cancer. Subjects will be scheduled to participate  $\geq 1$  month from travel outside the central time zone, and during a time with minimal special events.

#### **STUDY-WIDE NUMBER OF PARTICIPANTS:**

N/A Northwestern University is the only site where recruitment and participation in study will occur.

#### **STUDY-WIDE RECRUITMENT METHODS:**

N/A Northwestern University is the only site where recruitment and participation in study will occur.

#### **MULTI-SITE RESEARCH:**

N/A Northwestern University is the only site where recruitment and participation in study will occur.

#### **STUDY TIMELINES:**

The protocol will last 6-10 weeks depending on how soon after consent the subject can participate. We aim to complete recruitment by 05/31/2018 and primary data analysis by 05/31/2019.

#### **STUDY ENDPOINTS:**

The goal of this research project is to test a novel behavioral intervention, morning light treatment, to see if it can improve glucose metabolism in people with prediabetes.

## Primary Outcomes:

**Outcome 1:** We will determine the effect of active versus placebo morning light treatment on glucose metabolism in individuals with prediabetes.

[figure not shown]
**Outcome 2:** We will determine the extent to which circadian phase advances in the DLMO are related to improvements in glucose metabolism in individuals with prediabetes.

## PROCEDURES INVOLVED:

Figure 3 presents an overview of the 5 week protocol. After screening for eligibility (see below) and informed consent, subjects will wear a wrist actigraph throughout the study. Subjects will complete a daily sleep and medication log, a questionnaire packet, and a 3-day food diary at the end of the baseline week and week 4. After the baseline week, there will be an overnight stay at the Northwestern University Clinical Research Center. Questionnaires and food diaries will be reviewed and body fat via bioimpedance will be measured. The DLMO will be assessed.

Subjects will be given dinner 4 h before bedtime and consumed 3 hours prior to bedtime to ensure duration of fasting is at least 8 h and does not exceed 14 h. In the morning, a 3 hour oral glucose tolerance test (OGTT) will be performed in the Clinical Research Unit (CRU) 2 h after wake. Subjects will then begin a 4 week morning light treatment (see details below). The first 10 subjects will be assigned active (bright), and the following 5 will be assigned placebo (dim) Re-timer®. If more subjects are enrolled in the study, the next 10 will be placed on active (bright) treatment. Subjects will receive feedback on their compliance at weekly visits. Subjects will be paid \$95 in cash at each visit to increase likelihood of participation and retention. In the final week, subjects will complete questionnaires and food diaries again. After the 4 week treatment, subjects will repeat the laboratory session for reassessment of the DLMO and OGTT.

Figure 3. Protocol Overview

**Subjects and Screening.** As a first step in testing morning light treatment to improve glucose metabolism, we will enroll a sample of 34 subjects (50% female, ages 35-75 years), who are most likely to benefit from morning light. These subjects will: (1) be obese ( $BMI \geq 25 \text{ kg/m}^2$ ), (2) have prediabetes ( $HbA1c 5.7\% \text{ to } < 6.5\%$ ), and (4) be free of severe obstructive sleep apnea (apnea-hypopnea index  $< 30$ ). Subjects will be screened initially over the phone or by completing the screening survey online via RedCap, and be asked to begin recording their bed times and wake times to determine the schedule for their light treatment. If potentially eligible, they will be invited to a pre-study screening visit, during which height and weight and  $HbA1c$  (finger stick of blood) will be assessed. Subjects will also need to pass a urine drug screen. [name], a board-certified endocrinologist (co-investigator), will refer any subjects who are identified as having diabetes, for treatment. Any subjects identified as having prediabetes will also be

referred to treatment, but also invited to participate in the final home screen for obstructive sleep apnea. Note that subjects who begin prediabetes treatment prior to the end of the study will be dropped, however, due to common delays in seeing a physician (over a month), this is unlikely to affect many subjects (as part of intent-to-treat analysis the last observation will be carried over). Subjects will be instructed in the use of the WatchPAT™ device (Itamar Medical Ltd.) to screen for obstructive sleep apnea. WatchPAT utilizes Peripheral Arterial Tone (PAT), a physiological signal that mirrors changes in the autonomic nervous system caused by respiratory disturbances during sleep. The automatic algorithm of WatchPAT analyzes the PAT signal amplitude along with heart rate and oxygen saturation to identify respiratory events and provide AHI. [name], who is board certified in sleep medicine and a consultant on this grant, will oversee the interpretation of the home sleep screen. Any subject with an apnea-hypopnea index  $\geq 15$  will be informed of the result by study investigators and offered referral to a nearby sleep center for treatment and excluded from study participation.

Laboratory sessions will occur during women's follicular phase or women will be postmenopausal ( $\geq 6$  months since last menses). Women on oral contraceptives or hormone replacement therapy will be excluded (alters OGTT and melatonin). Additional exclusion criteria include: history of any form of diabetes, smokers, shift workers, eye disease, photosensitizing medications, regular hypnotic use ( $\geq 3$  nights/week) daily beta-blocker, NSAID or melatonin use (confounds DLMO), history of psychiatric disorders (confounds light treatment), pregnancy/breastfeeding, irregular menses, history of cardiovascular disease (excluding hypertension), endocrine, kidney, GI or liver disorder, seizures, cancer. Recruitment will include advertising the study to current diabetes patients to recruit family members who may meet eligibility criteria. [name] sees over 350 diabetes patients each year. Recruitment will also include posting fliers, brochures, newspaper advertisements, and advertisements around Chicago, online, at various clinics in the Chicago area (as permitted by the local staff and healthcare providers) and attending community events. Note that recruitment at various clinics will involve only distributing flyers and brochures, but will not include sharing of patient information directly with us. Thus, the initial contact will be made by the volunteer.

**Light Treatment.** The 1 h daily morning light treatment will start within a few minutes after each subject's average wake time, as determined from the baseline week of actigraphy. The light treatment may start up to 1 h earlier to accommodate the subject's usual morning schedule (work, child care) if required. Subjects are provided with an alarm set to the start of the morning treatment. A light log to note light on/off times and any interruptions to the light treatment will be provided. Subjects will be instructed to maintain their baseline sleep duration throughout the light treatment. Daily bed and wake time phone calls to a time-stamped voice mail will be reviewed daily with phone calls to subjects if required to ensure compliance. Wrist actigraphy data will be reviewed weekly in the presence of the subject. Importantly, the Re-timer® light device is commercially available. The adjustable nose pad on each Re-timer® (whether active or placebo) will be individually fit to each subject to optimize the light treatment (Appendix). After the introduction to the Re-timer® (whether active or placebo), subjects will complete a treatment expectation item of 0 "expect no change" to 10 "expect to be healthier". In between weekly visits, subjects will be encouraged to call research staff 24/7 with any questions about the light treatment. At the start of the second laboratory session, subjects will complete a treatment satisfaction item of 0 "not at all satisfied" to 10 "extremely satisfied".

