#### **DATA AND SPECIMEN MANAGEMENT:**

##### **Sample Size and Power Analysis**

We plan to enroll 34 subjects (50% female, age 35-70 y) with prediabetes. We conservatively estimate a 17% attrition rate (final n=28) which includes dropouts and noncompliance (noncompliance defined as <25% of morning light treatment, as per). This attrition rate is based on [name] light treatment trials (5% such attrition), and the work of others (4 week bright light treatment group 6% attrition, 12 week bright light treatment group 19% attrition). Note that subjects who obtain only 25% of the prescribed active light (e.g. 15 min/day) are likely to obtain some benefit, as even only 15-20 mins of morning light can be clinically effective, and only a 12 min pulse can shift the DLMO.

A primary goal of this project is to determine the effect sizes associated with morning light treatment to develop a larger RCT. However, for this pilot project we also estimated the required sample size to detect a clinically meaningful change in our primary outcome measure, fasting glucose level. We will also measure 2-h glucose and MI from the OGTT but have kept fasting glucose level as our primary outcome measure as it is a commonly used clinical measure. To estimate sample size for fasting glucose, we used a standard deviation (SD) of 9.0 mg/dl, which is the mean SD in a large sample of men and women with prediabetes. Using these values for a two-tailed independent t-test, with a total of 14 subjects per group, we will have 81% power ( $\alpha=.05$ ) to detect a change of 10 mg/dl, which is a clinically meaningful change and similar to that observed in a 2-week drug study. Thus we are well powered with an anticipated final sample size of n=28 to detect a clinically meaningful change in fasting glucose.

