#### **Data Analysis**

**Aim 1:** For our primary analyses, we will examine the effect sizes in active treatment group. The analysis will use two-sided statistical tests and a nominal significance of 5%. Our primary analysis will focus on the pre-post measurements in the active group. As a descriptive analysis, we will estimate the mean outcome measures at each time point for each subject and test time-specific differences using non-parametric tests. If we recruit sufficient subjects for the placebo condition, we will compare the effects in the two groups.

**Aim 2:** To determine the extent to which circadian phase advances in the DLMO are related to improvements in glucose metabolism, we will first examine if the DLMO has changed significantly in the active light treatment group (and compared to placebo if possible), and then

examining if these differences are correlated with changes in glucose metabolism measures.

**Exploratory Aim:** In a similar analysis to Aim 2, we will examine possible alternative mediators (body fat, activity, total caloric intake, and sleep fragmentation [wrist actigraphy]) through which morning light treatment may impact glucose metabolism (fasting glucose, 2-h glucose, MI). We will measure body fat because it was reduced in two previous light studies (reviewed in A.2.). We will measure physical activity because light treatment has an energizing effect . We will assess total caloric intake, as differences in circadian timing can impact diet . We do not expect changes in sleep duration as subjects will be instructed to maintain their habitual sleep duration during the treatment. However, a shift in circadian timing can impact sleep consolidation  so we will assess sleep fragmentation from wrist actigraphy.

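### Arm is set by enrolment order (1–10 active, 11–15 placebo, 16–25 active), so the active-versus-placebo comparison is non-randomised, predictable and open to calendar-time bias

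*Combined protocol and SAP*

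**What the plan says.** Under Procedures Involved, the arm follows from the subject's place in the queue: "The first 10 subjects will be assigned active (bright), and the following 5 will be assigned placebo (dim"). It continues: "If more subjects are enrolled in the study, the next 10 will be placed on active (bright) treatment". The safety-monitoring section says only that subjects will be assigned to one of two groups. Randomisation is mentioned only for a later, larger trial (Sample Size and Power Analysis; Potential Benefits).

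Three other sections depend on how the groups are formed:

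- Primary Outcomes, Outcome 1: "We will determine the effect of active versus placebo morning light treatment on glucose metabolism in individuals with prediabetes".
- Sample Size and Power Analysis: a two-sided independent t-test "with a total of 14 subjects per group", and the statement "A primary goal of this project is to determine the effect sizes associated with morning light treatment to develop a larger RCT".
- Data Analysis, Aim 1: "Our primary analysis will focus on the pre-post measurements in the active group", followed by "If we recruit sufficient subjects for the placebo condition, we will compare the effects in the two groups". Aim 2 likewise compares the melatonin-onset (DLMO) change with placebo if possible.

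No section describes a random sequence, allocation concealment, or adjustment for calendar time or season.

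**The concern.** Allocation by enrolment order raises two problems.

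**Time.** Each arm is recruited in its own block. Anything that changes between blocks (season, recruitment source, staff practice, assay batch) is confounded with treatment. Season is a natural worry in a light trial, and the protocol's Background cites a light-exposure study that adjusted for it.

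**Predictability.** Anyone who knows the rule and the current count knows the next assignment before the subject is enrolled. The documents do not say who holds the rule. The placebo device looks identical to the active one, which may mask subjects, but it does not conceal the next assignment from recruiting staff.

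At stake is what Outcome 1 can support. A difference between groups could reflect period or selection as well as light. If it is carried forward as an effect size, the larger trial would be planned on a confounded estimate.

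**Working it through.** **Inputs from the documents.** Sequence of 10 active, 5 placebo, then 10 active (Procedures Involved). SD 9.0 mg/dl, difference 10 mg/dl, 14 per group, two-sided 5%, stated power 81% (Sample Size and Power Analysis). Version date 3 May 2018; recruitment target 31 May 2018 (Study Timelines).

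**1. The plan's own figure.** The noncentral t with 14 v 14, difference 10 and SD 9 gives 80.8%, which agrees with the stated 81%. With the same inputs and the arm sizes that the rule produces, power is 46.8% at 10 v 5 and 56.7% at 20 v 5, before attrition. This is a separate sample-size matter, but it shows that the rule and the power statement describe different designs.

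**2. Enrolment position by arm.**

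| Enrolled | Mean position, active | Mean position, placebo | Correlation of arm with position |
|---|---|---|---|
| 15 | (1+…+10)/10 = 5.5 | (11+…+15)/5 = 13.0 | −0.82 |
| 25 | (10×5.5 + 10×20.5)/20 = 13.0 | 13.0 | 0 |

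At 15 subjects the arms do not overlap. The share of a first-to-last linear drift that enters the comparison is (13.0 − 5.5)/(15 − 1) = 7.5/14 = 54%. At 25 it is zero. However, the correlation of arm with squared distance from the midpoint is then 0.54, so change that is not linear in time remains.

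**3. Seasonal change (assumed form).** Suppose four-week change follows a yearly sine of amplitude A, enrolment is even over T months, and the phase is the worst possible. Bias as a multiple of A is:

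| T (months) | 6 | 9 | 12 | 18 | 24 |
|---|---|---|---|---|---|
| 15 subjects | 1.27 | 1.43 | 1.25 | 0.65 | 0.64 |
| 25 subjects | 0.43 | 0.83 | 1.17 | 1.35 | 0.96 |

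These are upper bounds. At T = 3 months the 25-subject figure falls to about 0.12.

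**4. Effect on the 5% error (assumed block differences).** SD of change = 9√(2(1−ρ)). An assumed ρ of 0.5 to 0.7 gives 9.0 to 7.0 mg/dl. With no light effect and a block difference b in four-week change, the noncentrality is b/(SD√(1/n₁+1/n₂)). Two-sided rejection rates are:

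| b (mg/dl) | 10 v 5 | 20 v 5 |
|---|---|---|
| 3 | 8.7–11.3% | 9.8–13.1% |
| 5 | 15.6–22.9% | 18.7–28.0% |

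The 20 v 5 column also assumes that both active blocks share one mean.

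**5. Predictability.** Under the current rule 100% of assignments are known in advance to anyone who knows it. For a 2:1 random list in fixed blocks of 3, the number deducible from past assignments is 2, 1 or 1 for the three equally likely orders, so 4/9 = 44%. For blocks of 3 or 6, equally likely and with size hidden, simulation over 15 subjects gives 9%.

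**6. Precision after a change.** The standard-error factor is √(1/n₁+1/n₂). At 20 v 5 it is 0.500. If 25 subjects were randomised 2:1 from the start (17 v 8) it is 0.429. If the first 10 are already active, randomising the next 15 at 2:1 gives 20 v 5 overall (0.500), and the randomised part alone is 10 v 5 (0.548). If 15 are already assigned, about 7 v 3 remain (0.69).

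**The case against.** The best defence is that the comparison is secondary in practice. This is a pilot, the analysis section makes the pre-post change in the active group primary and looks for effect sizes there, and groups are compared only if placebo recruitment suffices. The rule is stated openly and the study is never called randomised. Many eligibility criteria are measured (HbA1c, BMI, apnoea index, drug screen) and the outcome is a laboratory value, which narrows the room for selection. No start date, accrual rate or seasonal effect is given, so the size of the bias is assumed. With recruitment nearly over, randomising the remainder may add little.

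Much of this stands. The order does not affect the pre-post analysis, the bias figures are illustrations, and predictability alone does not show that selection occurred. But the pre-post analysis has no concurrent control, so the placebo group is the only check on time, expectation and regression to the mean. Outcome 1 still promises an active-versus-placebo effect. Disclosing the rule under Procedures Involved is not a caveat where the comparison is defined and analysed. Measured criteria and a laboratory outcome do nothing about confounding with period.

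**Conclusion.** The concern holds and should be fixed. From the documents alone, assignment is by enrolment order, fully predictable from the rule, and at 15 subjects completely aliased with period. At 25 subjects linear drift cancels but other time patterns do not. How large the bias is cannot be derived from the documents. If four-week change differed by 3 to 5 mg/dl between blocks, with an SD of change of 7–9 mg/dl, the nominal 5% error would be roughly 9–28% across the two arm-size scenarios. The finding limits what Outcome 1, the conditional group comparison in Aim 1 and the placebo comparison in Aim 2 can support. It does not bear on the active-group pre-post estimate, whose weakness is the lack of any control.

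**What to change.** 1. **Subjects already assigned by order.** State under Primary Outcomes and Data Analysis that the between-group comparison is non-randomised and descriptive, and is not to be read as the effect of light or used alone as the effect size for the larger trial. Report these subjects separately from any who are randomised.
2. **Subjects not yet assigned.** Use a concealed, computer-generated list with randomly varied block sizes, held by someone not involved in enrolment, device fitting or compliance feedback, so that the arms are interleaved in time. At 2:1, mixed blocks of 3 and 6 would serve.
3. **One ratio first.** The rule implies 2:1 at 15 subjects and 4:1 at 25, and gives no assignment for subjects 26 to 34. The power statement assumes 14 per group. Reconcile these before drawing up the list.
4. **No claim of added precision**, since any gain depends on how many subjects remain unassigned.

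The cost is one amendment and one list; both device types already exist. Slightly fewer active subjects accrue if enrolment stops early. The plan states "We aim to complete recruitment by 05/31/2018", 28 days after the date of this version, so most subjects may already be assigned. If none remain, only the wording change in step 1 applies.
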